11.6 Appendix 6. Sample Storage and Destruction

Any blood or tissue (eg, PK, biomarker) samples collected according to the Schedule of Activities can be analyzed for any of the tests outlined in the protocol and for any tests necessary to minimize risks to study subjects. This includes testing to ensure analytical methods produce reliable and valid data throughout the course of the study. This can also include, but is not limited to, investigation of unexpected results, incurred sample reanalysis, and analyses for method transfer and comparability.

All samples and associated results will be coded prior to being shipped from the site for analysis or storage. Samples will be tracked using a unique identifier that is assigned to the samples for the study. Results are stored in a secure database to ensure confidentiality.

If informed consent is provided by the subject, Amgen can do additional testing on remaining samples (ie, residual and back-up) to investigate and better understand the inflammatory conditions, the dose response and/or prediction of response to efavaleukin alfa, characterize antibody response, and characterize aspects of the molecule (eg, mechanism of action/target, metabolites). Results from this analysis are to be documented and maintained, but are not necessarily reported as part of this study. Samples can be retained for up to 20 years.

Since the evaluations are not expected to benefit the subject directly or to alter the treatment course, the results of pharmacogenetic, or other exploratory studies are not placed in the subject's medical record and are not to be made available to the subject, members of the family, the personal physician, or other third parties, except as specified in the informed consent.

The subject retains the right to request that the sample material be destroyed by contacting the investigator. Following the request from the subject, the investigator is to provide the sponsor with the required study and subject number so that any remaining blood and tissue samples and any other components from the cells can be located and destroyed. Samples will be destroyed once all protocol-defined procedures are completed. However, information collected from samples prior to the request for destruction, will be retained by Amgen.

The sponsor is the exclusive owner of any data, discoveries, or derivative materials from the sample materials and is responsible for the destruction of the sample(s) at the request of the subject through the investigator, at the end of the storage period, or as

appropriate (eg, the scientific rationale for experimentation with a certain sample type no longer justifies keeping the sample). If a commercial product is developed from this research project, the sponsor owns the commercial product. The subject has no commercial rights to such product and has no commercial rights to the data, information, discoveries, or derivative materials gained or produced from the sample. See Section 11.3 for subject confidentiality.

11.7 Appendix 7. Hepatotoxicity Stopping Rules: Suggested Actions and Follow-up Assessments and Study Treatment Rechallenge Guidelines

Subjects with abnormal hepatic laboratory values (ie, alkaline phosphatase [ALP], aspartate aminotransferase [AST], alanine aminotransferase [ALT], total bilirubin [TBL]) and/or international normalized ratio (INR) and/or signs/symptoms of hepatitis (as described below) may meet the criteria for withholding or permanent discontinuation of Amgen investigational product or other protocol-required therapies, as specified in the Guidance for Industry Drug-Induced Liver Injury: Premarketing Clinical Evaluation, July 2009.

Criteria for Withholding and/or Permanent Discontinuation of Amgen Investigational Product and Other Protocol-required Therapies Due to Potential Hepatotoxicity

The following stopping and/or withholding rules apply to subjects for whom another cause of their changes in liver biomarkers (TBL, INR and transaminases) has not been identified.

Important alternative causes for elevated AST/ALT and/or TBL values include, but are not limited to:

- Hepatobiliary tract disease
- Viral hepatitis (eg, hepatitis A/B/C/D/E, Epstein-Barr Virus, cytomegalovirus, herpes simplex virus, varicella, toxoplasmosis, and parvovirus)
- Right sided heart failure, hypotension or any cause of hypoxia to the liver causing ischemia
- Exposure to hepatotoxic agents/drugs or hepatotoxins, including herbal and dietary supplements, plants and mushrooms
- Heritable disorders causing impaired glucuronidation (eg, Gilbert's syndrome, Crigler-Najjar syndrome) and drugs that inhibit bilirubin glucuronidation (eg, indinavir, atazanavir)
- Alpha-one antitrypsin deficiency
- Alcoholic hepatitis
- Autoimmune hepatitis
- Wilson's disease and hemochromatosis
- Nonalcoholic fatty liver disease including steatohepatitis
- Non-hepatic causes (eg, rhabdomyolysis, hemolysis)

If investigational product(s) is/are withheld, the subject is to be followed for possible drug induced liver injury (DILI) according to recommendations in the last section of this appendix.

Rechallenge may be considered if an alternative cause for impaired liver tests (ALT, AST, ALP) and/or elevated TBL, is discovered and the laboratory abnormalities resolve to normal or baseline (see next section in this appendix).

Table 11-3. Conditions for Withholding and/or Permanent Discontinuation of Amgen Investigational Product and Other Protocol-required Therapies Due to Potential Hepatotoxicity

Analyte	Temporary Withholding	Permanent Discontinuation
TBL	> 3x ULN at any time	> 2x ULN OR
INR	--	> 1.5x (for subjects not on anticoagulation therapy) AND
AST/ALT	> 8x ULN at any time > 5x ULN but < 8x ULN for ≥ 2 weeks > 5x ULN but < 8x ULN and unable to adhere to enhanced monitoring schedule > 3x ULN with clinical signs or symptoms that are consistent with hepatitis (such as right upper quadrant pain/tenderness, fever, nausea, vomiting, and jaundice)	In the presence of no important alternative causes for elevated AST/ALT and/or TBL values > 3x ULN (when baseline was < ULN)
ALP	> 8x ULN at any time	--

ALP = alkaline phosphatase; ALT = alanine aminotransferase; AST = aspartate aminotransferase; INR = international normalized ratio; TBL = total bilirubin; ULN = upper limit of normal

Criteria for Rechallenge of Amgen Investigational Product and Other Protocol-required Therapies After Potential Hepatotoxicity

The decision to rechallenge the subject is to be discussed and agreed upon unanimously by the subject, investigator, and Amgen.

If signs or symptoms recur with rechallenge, then efavaleukin alfa is to be permanently discontinued. Subjects who clearly meet the criteria for permanent discontinuation (as described in Table 11-3) are never to be rechallenged.

Drug-induced Liver Injury Reporting and Additional Assessments

Reporting

To facilitate appropriate monitoring for signals of DILI, cases of concurrent AST or ALT and TBL and/or INR elevation, according to the criteria specified in the above, require the following:

- The event is to be reported to Amgen as a serious adverse event within 24 hours of discovery or notification of the event (ie, before additional etiologic investigations have been concluded)

- The appropriate Case Report Form (CRF) (eg, Events eCRF) that captures information necessary to facilitate the evaluation of treatment-emergent liver abnormalities is to be completed and sent to Amgen

Other events of hepatotoxicity and potential DILI are to be reported as serious adverse events if they meet the criteria for a serious adverse event defined in Section 11.4.

Additional Clinical Assessments and Observation

All subjects in whom investigational product(s) or protocol-required therapies is/are withheld (either permanently or conditionally) due to potential DILI as specified in [Table 11-3](#) or who experience AST or ALT elevations $> 3 \times$ upper limit of normal (ULN) or 2-fold increases above baseline values for subjects with elevated values before drug are to undergo a period of “close observation” until abnormalities return to normal or to the subject’s baseline levels.

Assessments that are to be performed during this period include:

- Repeat AST, ALT, ALP, bilirubin (BIL) (total and direct), and INR within 24 hours
- In cases of TBL $> 2 \times$ ULN or INR > 1.5 , retesting of liver tests, BIL (total and direct), and INR is to be performed every 24 hours until laboratory abnormalities improve

Testing frequency of the above laboratory tests may decrease if the abnormalities stabilize or the investigational product(s) or protocol-required therapies has/have been discontinued AND the subject is asymptomatic.

Initiate investigation of alternative causes for elevated AST or ALT and/or elevated TBL.

The following are to be considered depending on the clinical situation:

- Complete blood count with differential to assess for eosinophilia
- Serum total immunoglobulin (Ig)G, anti-nuclear antibody anti-smooth muscle antibody, and liver kidney microsomal antibody-1 to assess for autoimmune hepatitis
- Serum acetaminophen (paracetamol) levels
- A more detailed history of:
 - Prior and/or concurrent diseases or illness
 - Exposure to environmental and/or industrial chemical agents
 - Symptoms (if applicable) including right upper quadrant pain, hypersensitivity-type reactions, fatigue, nausea, vomiting and fever
 - Prior and/or concurrent use of alcohol, recreational drugs and special diets
 - Concomitant use of medications (including non-prescription medicines and herbal and dietary supplements), plants, and mushrooms
- Viral serologies
- Creatine phosphokinase, haptoglobin, lactate dehydrogenase and peripheral blood smear

- Appropriate liver imaging if clinically indicated
- Appropriate blood sampling for pharmacokinetic analysis if this has not already been collected
- Hepatology consult (liver biopsy may be considered in consultation with a hepatologist)

Follow the subject and the laboratory tests (ALT, AST, TBL, INR) until all laboratory abnormalities return to baseline or normal or considered stable by the investigator. The "close observation period" is to continue for a minimum of 4 weeks after discontinuation of all investigational product(s) and protocol-required therapies.

The potential DILI event and additional information such as medical history, concomitant medications and laboratory results must be captured in the corresponding eCRFs.

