224 Subjects who have received live vaccines within 5 weeks prior to screening, or plan to receive live vaccines during the treatment period and up to 6 weeks after the last dose of investigational product in the study.

225 Has received any of the following prescribed medication or therapy within the specified time period:

- Anti-TNF antibodies (eg, infliximab, adalimumab, golimumab) ≤ 8 weeks prior to screening endoscopy
- Anti-integrin antibodies (eg, vedolizumab) < 8 weeks prior to screening endoscopy
- IL-12/23 antagonist (eg, ustekinumab) < 8 weeks prior to screening endoscopy
- JAK inhibitors (eg, tofacitinib) < 4 weeks prior to screening endoscopy
- S1P modulators (eg, ozanimod) < 4 weeks prior to screening endoscopy.

- Any other commercially approved biologic agent or targeted small molecule \leq 8 weeks prior to screening endoscopy or $<$ 5 half-lives prior to screening endoscopy, whichever is longer
- Immunomodulatory medications oral cyclosporine, IV cyclosporine, tacrolimus, sirolimus, mycophenolate mofetil, thalidomide $<$ 4 weeks prior to screening endoscopy
- Any investigational biologic therapy within 8 weeks prior to screening endoscopy or $<$ 5 half-lives prior to screening endoscopy, whichever is longer
- Have used apheresis (eg, Adacolumn[®] apheresis) $<$ 2 weeks prior to screening endoscopy

Diagnostic Assessments

226 Abnormal laboratory results at screening:

- aspartate aminotransferase (AST) or alanine amino transferase (ALT) at screening $>$ 1.5 X upper limit of normal (ULN)
- serum total bilirubin (TBL) \geq 1.5 mg/dL (\geq 26 μ mol/L)
 - Subjects with established diagnosis of Gilbert's syndrome are allowed if TBL \leq 3X ULN (source documentation demonstrating unconjugated hyperbilirubinemia and no evidence of hemolysis required).
- hemoglobin \leq 8.5 g/dL (\leq 85 g/L)
- platelet count $<$ 100 000/mm³ ($<$ 100 \times 10⁹/L)
- white blood cell count $<$ 3000 cells/mm³ ($<$ 3.0 \times 10⁹/L)
- absolute neutrophil count (ANC) $<$ 1500/mm³ ($<$ 1.5 \times 10⁹/L)

227 Any other laboratory abnormality, which, in the opinion of the investigator, poses a safety risk, will prevent the subject from completing the study, will interfere with the interpretation of the study results, or might cause the study to be detrimental to the subject.

Prior/Concurrent Clinical Study Experience

228 Currently receiving treatment in another investigational device or drug study

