6.2.3 Hepatotoxicity Stopping and Rechallenge Rules

Refer to Section 11.7 for details regarding drug-induced liver injury guidelines, as specified in the Guidance for Industry Drug-Induced Liver Injury: Premarketing Clinical Evaluation, July 2009.

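### Table 11-3's permanent liver stop applies only if baseline AST/ALT was below ULN, which leaves an asymptomatic band with no mandatory hold or stop for subjects whose pre-dose baseline was higher

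*Protocol*

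**What the plan says.** **Entry.** Exclusion criterion 226 (Protocol Section 5.2) bars "aspartate aminotransferase (AST) or alanine amino transferase (ALT) at screening" only above 1.5x ULN. Values from ULN to 1.5x ULN are therefore eligible.

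**Stopping rule.** Protocol Section 6.2.3 contains no rule of its own: "Refer to Section 11.7 for details regarding drug-induced liver injury guidelines". Appendix 7 opens by limiting its scope: "The following stopping and/or withholding rules apply to subjects for whom another cause of their changes in liver biomarkers" has not been found. In the permanent-discontinuation column of Table 11-3, bilirubin above 2x ULN or INR above 1.5 must be combined with AST/ALT "> 3x ULN (when baseline was < ULN". No AST/ALT threshold is given for a baseline at or above ULN.

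**Temporary hold.** The other column applies at any baseline. It requires a hold for:
- bilirubin above 3x ULN;
- AST/ALT above 8x ULN;
- AST/ALT between 5x and 8x ULN for 2 weeks or more, or when enhanced monitoring is not possible;
- AST/ALT "> 3x ULN with clinical signs or symptoms that are consistent with hepatitis";
- ALP above 8x ULN.

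INR has no hold entry.

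**Elevated baselines elsewhere in Appendix 7.** The close-observation paragraph provides for "2-fold increases above baseline values for subjects with elevated values before drug", but it requires retesting and a search for causes, not a stop.

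**The concern.** A combined rise in transaminases and bilirubin or INR with no other explanation is the pattern the permanent rule exists to catch. The same on-study values end treatment for a subject who started below ULN, yet need not interrupt it for one who started at or slightly above ULN. The appendix foresees subjects with raised pre-dose values, because it gives them their own observation trigger, but the permanent column leaves them out.

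Such subjects are plausible here. Criterion 107 lets azathioprine, 6-mercaptopurine and methotrexate continue at stable doses, and criterion 106 names liver test abnormalities among the intolerances to immunomodulators. At stake is whether the next dose is stopped by rule or only by judgement while the cause is unknown.

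**Working it through.** There is no plan figure to reproduce; the check is of the rule's logic.

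**Notation.** b is baseline AST/ALT, A is on-study AST/ALT and T is total bilirubin, all in multiples of ULN; I is INR. All cases assume no alternative cause, no hepatitis sign, ALP no higher than 8x ULN and monitoring possible, unless stated.

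**Rules from Table 11-3.**
- Permanent: (T > 2 or I > 1.5) and A > 3 and b < 1.
- Hold: T > 3; or A > 8; or 5 < A < 8 for 2 weeks or more; or 5 < A < 8 without monitoring; or A > 3 with a hepatitis sign; or ALP > 8x ULN.

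**The uncovered band.** If b is 1 or more, the permanent rule is never true. No hold applies when T is 3 or less and either A is 5 or less, or 5 < A < 8 for under 2 weeks. Adding the combined-elevation condition (A > 3 with T > 2 or I > 1.5) gives:
- AST/ALT: 3 < A ≤ 5 for any duration, or 5 < A < 8 for under 2 weeks; together with
- bilirubin or INR: 2 < T ≤ 3, or I > 1.5 with T ≤ 3.

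**Illustrative value sets** (I = 1.0 unless stated):

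| Set | A | T | Duration | b = 0.8 | b = 1.3 |
|---|---|---|---|---|---|
| 1 | 4.5 | 2.5 | under 2 weeks | permanent | neither |
| 2 | 4.5 | 2.5 | 2 weeks or more | permanent | neither |
| 3 | 4.5 | 1 (I = 1.6) | any | permanent | neither |
| 4 | 7 | 2.5 | under 2 weeks | permanent | neither |
| 5 | 7 | 2.5 | 2 weeks or more | permanent | hold only |
| 6 | 4.5 | 3.5 | any | permanent | hold only |
| 7 | 8.5 | 2.5 | any | permanent | hold only |

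Results at b = 1.0 and b = 1.5 match those at 1.3: four sets meet neither column and three are held. With a hepatitis sign present at b = 1.3, all seven are held.

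**Which value is baseline.** Appendix 7 does not define it. Table 1-1 repeats chemistry on day 1, Section 8.1.1 allows two screening retests, and SAP Section 5.2 takes the last value before first dose. The 1.5x limit applies to screening only, so b can be below 1 in a subject screened above ULN, and can also exceed 1.5.

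**Comparing two fixes.**
- Deleting the bracket gives a threshold of A > 3 at every baseline.
- A baseline-relative limb for b of 1 or more requires A > 3 and A ≥ 2b.
- For b from 1.0 to 1.5, 2b runs from 2.0 to 3.0, so A > 3 already implies more than a 2-fold rise and the fixes agree. At b = 1.3 the smallest A in the table gives 4.5/1.3 = 3.5-fold, and all seven sets become permanent under either fix.
- For b = 1.8, 2b = 3.6. At A = 3.1 the rise is 3.1/1.8 = 1.7-fold. With T > 2, deletion would force a permanent stop and the limb would not.

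**Doses at issue.** The dosing interval is redacted. Suppose A stays in the 3x to 5x part of the band from day 29 and remains unexplained.
- 14-day interval, assumed from the SAP exposure window (Section 5.1): doses on days 1, 15, 29, 43, 57 and 71, so 3 later induction doses are not stopped by the table.
- 28-day interval: doses on days 1, 29 and 57, so 1 later dose.

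In the 5x to 8x part the hold arrives at 2 weeks. Section 6.1.1 allows doses 7 days apart, so one could fall before it.

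**The case against.** **Existing controls are substantial.** AST/ALT above 3x ULN brings close observation, a repeat panel within 24 hours and a search for causes. Retesting is then every 24 hours while bilirubin exceeds 2x ULN or INR exceeds 1.5, though less often if values stabilise. Section 7 lets the investigator or sponsor stop product, and a DMC reviews safety. The list of hepatitis signs is open-ended and includes jaundice, which narrows the bilirubin part of the band. All of this stands. It limits the harm, but none of it obliges anyone to withhold the next dose in the band.

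**The qualifier may be deliberate.** From a raised baseline, 3x ULN is a smaller relative rise. That supports a different threshold for these subjects; it does not support having none.

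**Outside guidance.** Sections 6.2.3 and 11.7 cite a 2009 industry guidance that cannot be consulted here. Sites apply the table as printed, so the citation does not fill the missing entry.

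**The examples are worst cases.** The value sets were chosen to show where the columns differ, and the dose count needs an unexplained elevation to persist for weeks with nobody acting. The INR route is narrower still: coagulation is scheduled only on day 1, so a later INR would normally come from close observation or extra testing. This is accepted. The four of seven is not a frequency, and the dose counts are not risk estimates.

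**Severity.** The affected number is unknown, and SAP Section 11 reports termination for futility, so no planned analysis changes. That limits the practical reach but does not alter the defect in a safety rule that is cheap to repair.

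**Conclusion.** The gap is real and narrow, and it should be closed. As written, a subject with a pre-dose baseline at or above ULN can have an unexplained, asymptomatic combined elevation that requires neither hold nor stop, although the same values would be permanent discontinuation from a baseline below ULN. This rests on reading the permanent column as (bilirubin or INR) and AST/ALT, and on baseline meaning the last pre-dose value. How many subjects fall in the band cannot be derived from the documents.

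Four stronger readings are tempting but unsupported:
- **That every subject screened between ULN and 1.5x ULN is exposed.** The table turns on baseline, and someone back below ULN on day 1 is fully covered.
- **That these subjects are unprotected or could readily be rechallenged.** Observation and discretionary stopping apply. After a hold, "Rechallenge may be considered if an alternative cause for impaired liver tests (ALT, AST, ALP) and/or elevated TBL, is discovered", and then only if values resolve and the subject, investigator and sponsor all agree.
- **That expedited reporting is lost as well.** It covers "cases of concurrent AST or ALT and TBL and/or INR elevation, according to the criteria specified in the above", which can be read with or without the baseline condition.
- **That simply deleting the bracket is an equivalent remedy.** It is equivalent only for baselines up to 1.5x ULN.

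**What to change.** Keep the existing AST/ALT cell in the permanent-discontinuation column and add a second limb: for baseline at or above ULN, AST/ALT above 3x ULN and at least 2x baseline. Define baseline in Appendix 7 as the last value before first dose. The factor of 2 matches the appendix's own observation trigger; the sponsor's medical team should confirm it. Optionally, add a sentence saying that the 24-hour reporting requirement applies at any baseline.

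The cost is one table cell and a definition, with no added visit, test or procedure. A few more subjects might be permanently discontinued, and under SAP Section 9.5.2 those stopped by the end of induction count as not meeting the endpoint. With a baseline above 1.5x ULN, values above 3x ULN but below twice baseline would still rest on observation and judgement. Because this trial has been terminated, the sponsor should also check whether the same cell appears in the extension study named in Protocol Section 4.1.2, whose protocol is not available here.

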11.8 Appendix 8. Prohibited Medications

This section outlines medications that are prohibited during the treatment phase of the study, including windows for prohibited medications prior to the screening endoscopy, if applicable.

Drug Class	Medication Restrictions
Anti-TNF antibodies (eg, infliximab, adalimumab, golimumab)	Discontinue at least 8 weeks prior to screening endoscopy and prohibited unless the subject has stopped investigational product permanently
Anti-integrin antibodies (eg, vedolizumab)	Discontinue at least 8 weeks prior to screening endoscopy and prohibited unless the subject has stopped investigational product permanently
IL-12/23 antagonist (eg, ustekinumab)	Discontinue at least 8 weeks prior to screening endoscopy and prohibited unless the subject has stopped investigational product permanently
JAK inhibitors (eg, tofacitinib)	Discontinue at least 4 weeks prior to screening endoscopy and prohibited unless the subject has stopped investigational product permanently
S1P modulators (eg, ozanimod)	Discontinue at least 4 weeks prior to screening endoscopy and prohibited unless the subject has stopped investigational product permanently
Any other commercially approved biologic agent or targeted small molecule	Discontinue at least 8 weeks prior to screening endoscopy or 5 half-lives prior to screening endoscopy, whichever is longer, and prohibited unless the subject has stopped investigational product permanently
Immunomodulatory medications oral cyclosporine, intravenous cyclosporine, tacrolimus, sirolimus, mycophenolate mofetil, or thalidomide	Discontinue at least 4 weeks prior to screening endoscopy and prohibited throughout duration of study
Any investigational biologic therapy	Discontinue at least 8 weeks prior to screening endoscopy or 5 half-lives prior to screening endoscopy, whichever is longer, and prohibited throughout duration of study
Apheresis (eg, Adacolumn® apheresis)	Discontinue at least 2 weeks prior to screening endoscopy and prohibited throughout duration of study

T cell depleting agents (eg, antithymocyte globulin, Campath).	Patients with exposure within 12 months prior to screening not eligible to be enrolled.
Recombinant IL-2 (eg, Proleukin®).	Patients with any previous exposure not eligible to be enrolled.
Corticosteroid enemas, corticosteroid suppositories, a course of IV corticosteroids or intramuscular corticosteroids, or oral budesonide standard formulation (not oral budesonide MMX)	Discontinue at least 2 weeks prior to screening endoscopy and prohibited unless the subject has stopped investigational product permanently
5-ASA enemas or 5-ASA suppositories	Discontinue at least 2 weeks prior to screening endoscopy and prohibited unless the subject has stopped investigational product permanently
Live vaccines	Last vaccination (if any) given at least 5 weeks prior to screening. Live vaccines are prohibited throughout the treatment period and for up to 6 weeks after the last dose of investigational product in the study.
Any other investigational therapies or device	Prohibited throughout duration of study.

Abbreviations: 5-ASA = 5-aminosalicylic acid; IL-2 = interleukin-2; IL-12/23 = interleukin 12/23; IV = intravenous; JAK = Janus Kinase; TNF = tumor necrosis factor; UC = ulcerative colitis.

